### **6.3 Randomization, Allocation of Patients**

Eligible subjects will be randomized into 3 cohorts based on their age:

Randomization Cohort 1: 48 patients 3 months to < 2 years of age

Randomization Cohort 2: 48 patients 2 years to < 12 years of age

Randomization Cohort 3: 48 patients 12 to 16 years of age

Within each cohort, subjects will be randomized at baseline in a 1:1 ratio to receive either Smoflipid or Intralipid 20%. Randomization will be implemented by the unblinded site pharmacist using [REDACTED] interactive web response system. Appropriate randomization codes will be provided on the screen immediately after randomization for a subject is requested. The assigned treatment code will be stored in [REDACTED].

[REDACTED] is a web based platform that integrates the most important functions of this clinical study, including patient enrollment, randomization and unblinding procedure, study drug management and accountability, eCRF and safety reporting. All individual functions of the platform are validated and CFR 21 Part 11 compliant.

Patients will be identified using a sequential numbering system. During the course of screening, the subject will be given a seven-digit number having an underscore following the first four digits. The first four digits of this number will be the site number. The last three digits will refer to the individual subject according to his/her sequence of entry into the study. For example, the first subject screened at site 0402 will be number 0402-001.

The unblinded site pharmacist will pick the study drug (either Smoflipid or Intralipid 20% in adequate bag size) as indicated by [REDACTED] for each randomized subject. The correctness of the picked study drug will be checked and confirmed by [REDACTED] based on the individual bag number, which the pharmacist will be required to type into the system. The unblinded site pharmacist will affix an additional label with the subject (randomization) number onto the bag of the study drug when dispensing.

### **6.4 Blinding and Decoding**

As this is a double-blind study, the allocation to the treatment groups will not be known by the Investigator and staff, patients and their relatives, or members of the Fresenius Kabi Clinical Research Department until completion of the study.

A bag ID list will be prepared and provided to Fresenius Kabi manufacturing operations for the production of uniquely numbered bag labels. Bag ID numbers from 000 001 to 100 000 will be randomly assigned to Smoflipid or Intralipid 20% to ensure that numbers are not indicative of study treatment.

Smoflipid and Intralipid 20% will be delivered to the hospital pharmacists in 100 mL, 250 mL, and 500 mL infusion bags, together with the appropriate documentation (e.g., Certificates of Analysis).

## Clinical Study Protocol SMOF-028-CP4 Smoflipid® (lipid injectable emulsion)

---

The bags will have a blinded label in accordance with the requirements of Good Clinical Practice (GCP) and Good Manufacturing Practice (GMP), and each bag will be labeled with an individual bag number. Both study drugs are white emulsions which precludes unblinding by visual inspection.

The bags are packed in cartons, with 10 bags containing the same product and bag size in one carton. The cartons will have unblinded labels attached identifying the product. They are delivered to the hospital research pharmacy; the pharmacist will be the only unblinded study team member (The pharmacist can delegate the study procedures to his/her staff; they also would be unblinded).

For the individual patient, the pharmacist will receive the randomization information from the system (group allocation: Smoflipid or Intralipid 20%) as described in Section 6.3. Information about the individual daily dosage will be provided from the prescription, and the pharmacist will choose the appropriate bag size for the individual patient to ensure that the daily lipid dosage can be administered from 1 bag per day.

The pharmacist will dispense the appropriate study drug bags to the blinded site personnel. For patients in the home care setting, study drugs will be provided for a full month, i.e., until the next site visit of the patient. In this case, the pharmacist will also hand out a study medication log and the corresponding dispensing labels to the patient. The dispensing labels have to be applied to the study medication log immediately when a bag is prepared for infusion.

Emergency subject unblinding will be managed in [REDACTED]. In the event an Investigator needs to unblind a study subject, authorized study personnel at the site will log into the appropriate [REDACTED] unblinding workflow, to request access to the unblinded randomization code for the subject in question. In order to do so, the Investigator will have to acknowledge the serious nature of unblinding. Upon taking these steps, [REDACTED] will then provide the Investigator the specific treatment arm for that subject. Upon exiting the unblinding workflow, an email notification of this action will automatically be sent to appropriate management and safety officials acknowledging the subject unblinding without providing the specific treatment arm. Note that this information will also be captured in the study audit trail, so it will be more secure than other forms of unblinding.

## 7. Data Management and Statistics

### 7.1 Data Management

This study will be monitored regularly by a Clinical Research Associate (CRA) as described in the Monitoring Manual and Electronic Case Report Form (eCRF) Completion Guidelines. The CRA will check for completion of the entries on the eCRFs, their compliance with the study protocol and GCP, and will compare the eCRF entries with the source data. A 100% source data verification and ICF check will be performed. In case of any data discrepancies,

## **Clinical Study Protocol SMOF-028-CP4**

### **Smoflipid® (lipid injectable emulsion)**

---

queries will be generated automatically by the system or manually by Data Management, the Medical Monitor, or the CRA. All eCRFs that have been completely monitored by the CRA will be signed electronically by the Investigator when all data queries have been resolved and Data Management has confirmed the eCRF is clean.

Data Management will process the data according to the Data Management Plan. The procedure of eCRF handling from the source up to submission to Data Management is described in Section 11.4.1.

## **7.2 Statistics**

### **7.2.1 Sample Size Estimation**

Sample size was defined as 144 patients (48 patients 3 months to < 2 years of age, 48 patients 2 years to < 12 years of age, and 48 patients 12 to 16 years of age), having completed Study Day 90. This is to ensure that at least 23 subjects are randomized to each treatment group within each age group.

Based on a presentation at the FDA's Pediatric Clinical Investigators Training in 2014, where it was noted that the minimum of 100 pediatric subjects is required to assess safety (Lewis 2014), the planned patient numbers (24 in each arm within each age group, or 144 total) are adequate to provide sufficient information on safety of pediatric dosing considering the low risk safety profile of Smoflipid in adults. The current study will enroll approximately 72 patients in the investigational group. Additional data for pediatric patients (neonates and infants) receiving Smoflipid will come from the clinical study started in December 2015 in the USA (see Section 4.1).

An exploratory study using descriptive statistical analysis of the target variables will be performed. There is no primary outcome parameter and the study is not powered. Reasons for this study design are explained in Section 6.2.

### **7.2.2 Analysis sets**

#### **Safety Set**

The safety population will consist of all patients having received at least one dose of a study drug and at least one post-baseline safety evaluation. The safety population will be used for analysis of safety variables.

#### **Intention-to-Treat Set**

The intention-to-treat (ITT) population will consist of all randomized patients.

#### **Per-Protocol Set**

The per-protocol (PP) population will consist of all randomized patients having received study drug at least until Study Day 90, with 5 to 7 infusions per week, and without any major protocol deviations (see Section 15.2).

## Clinical Study Protocol SMOF-028-CP4 Smoflipid® (lipid injectable emulsion)

---

ITT and PP populations will be used for analysis of efficacy variables.

### 7.2.3 Statistical Analysis

The study outcome measures were selected in order to assess the safety and nutritional efficacy of the PN lipid emulsion. No primary and secondary measures are defined. Outcome measures will be evaluated as they are documented. Laboratory values will be transformed into SI (Système International d'Unités) if necessary.

A comprehensive Statistical Analysis Plan (SAP), covering details of all methods used to analyze the various parameters will be prepared. It will also include information on the handling of missing values. The SAP will be reviewed, and if needed, updated before data analysis. The SAP will be approved and signed off prior to unblinding the study.

All target variables will be analyzed in an exploratory manner presenting descriptive statistics. Binary, categorical and ordinal parameters will be summarized by means of absolute and percentage numbers (including 'missing data' as valid category). Numerical data will be summarized by means of standard statistics (e.g., number of available data, mean, standard deviation, minimum, median, maximum, and lower and upper quartile). Confidence intervals (CI) will be determined within treatment for all outcome parameters for which mean and standard deviation will be calculated.

Wherever useful, the summary statistics will be presented by Study Day. Results will be presented stratified by study drug and age group, and overall. In addition, appropriate figures (e.g., bar charts, Box-Whisker-Plots) may be presented to summarize the results for some parameters also in a graphical way.

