**Duration of Treatment:**

Study treatment will last for a minimum of 90 consecutive days and as long as PN is indicated, up to 365 consecutive days. The study ends after the Final Study Visit, latest on Day 366 (see Section 1, Study Schedule). If the indication for PN continues after Study Day 365, PN will continue per normal institution policy. Study drugs will no longer be used.

Early termination of study treatment (Before Study Day 91)

The study treatment will stop if infusion of the study drug cannot be continued because TG or direct bilirubin levels remain above the defined limits (see above, Intravenous lipid dose management) after reduction of the dosage.

The study treatment will also be stopped if the Holman Index of a patient (biochemical marker for essential fatty acid deficiency (EFAD)) reaches or exceeds 0.4 or if any clinical symptoms of EFAD appear or when the patient's growth is inadequate (drop of 1 in z-score in a time period of 2 consecutive months).

The study treatment will also stop if enteral food tolerance increases and in consequence, less than 60% of the patient's

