### Safety variables:

- Incidence of PNALD/PNAC: Number of patients in each treatment group with direct bilirubin levels > 2 mg/dL, confirmed by a second sample collected 7 days after the first sample (incidence of PNALD/PNAC). Time from Study Day 1 until reaching direct bilirubin levels > 2 mg/dL, followed up by a second sample collected 7 days after the first sample (time of developing PNALD/PNAC). (i.e., presented as the Study Day on which for the first time the direct bilirubin level was found > 2 mg/dL.)
- Sterols in plasma including phytosterols:  $\beta$ -sitosterol, campesterol, stigmasterol, brassicasterol, ergosterol, cholesterol, desmosterol, lanosterol,  $\beta$ -sitostanol, lathosterol, squalene (a sterol precursor).
- Laboratory values: (blood, plasma, or serum): triglycerides, direct bilirubin, total bilirubin, alanine aminotransferase (ALT), aspartate aminotransferase (AST), gamma-glutamyl transferase (GGT), alkaline phosphatase (ALP), creatinine, urea nitrogen, electrolytes (Na, K, Mg, Cl, Ca, Phosphate), trace elements (ferritin, Zn, Se, Cu, Mn, Cr), glucose, total protein, C-reactive protein (CRP), white blood cells (WBC), red blood cells (RBC), and platelet counts, hemoglobin (hgb), hematocrit (hct), international normalized ratio (INR).
- Vital signs: blood pressure, heart rate, body temperature.
- All adverse events (AEs).
- The relation between genetic polymorphisms in the fatty acid desaturase genes FADS1 and FADS2 and plasma concentrations of linoleic acid,  $\alpha$ -linolenic acid, arachidonic acid, docosahexaenoic acid, eicosapentaenoic acid, and Mead acid, as well as relation to EFAD (triene/tetraene ratio).

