During the treatment phase, concomitant medications and all safety and efficacy parameters will be recorded according to the study schedule (see Section 11). All I.V. energy sources (study drugs, other PN components, propofol, dextrose from drug carrier solutions), enteral formulas, and oral intake will be documented daily to assure that total energy content from all sources does not exceed the prescribed caloric target. Changes in dosage of the study drugs or other PN components, and the reason for these changes will be recorded.

Study treatment will last for a minimum of 90 consecutive days and, as long as PN including lipids is indicated, up to 365 consecutive days. The study will be terminated if infusion of the study drug cannot be continued because of increased TG or direct bilirubin levels (see 10.3.4 Intravenous lipid dose management).

Up to Study Day 90 the study treatment will be terminated (i.e., early termination of study treatment) if less than 60% of the patient's energy requirements are provided by PN for at least

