### Stopping study drug infusion due to EFAD:

At each of the monthly visits blood samples will be drawn for the analysis of fatty acids in plasma and red blood cells. Based on the results the triene-tetraene ratio (Holman Index) will be calculated to assess EFAD. Severity of EFAD will be categorized according to Cober et al 2012:

Suspected EFAD:	Triene/tetraene ratio $\geq$ 0.05 and < 0.20
Moderate EFAD:	Triene/tetraene ratio $\geq$ 0.20 and < 0.40
Severe EFAD:	Triene/tetraene ratio $\geq$ 0.40

The site will be informed immediately as soon as severe EFAD is observed according to the Holman Index result and the patient must be permanently taken off study medication immediately. The investigators will also have to permanently discontinue study medication infusion in case clinical symptoms of EFAD are observed.

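### Adverse events get only counts and percentages although observation can run from days to 366 days; if mean stay differs by arm, this can create or hide a difference

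*Combined protocol and SAP*

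**What the plan says.** Section 5.2 lists all adverse events among the safety variables. Section 7.2.3 then covers every target variable with one rule: "All target variables will be analyzed in an exploratory manner presenting descriptive statistics". For categorical ones it adds: "Binary, categorical and ordinal parameters will be summarized by means of absolute and percentage numbers". Results are shown by study drug, by age group and overall, and by Study Day where that is useful. Confidence intervals are promised only for parameters that have a mean and standard deviation, so none is promised for an AE percentage. Further method detail is left to an SAP, to be signed off before unblinding, which is not part of the text available here.

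The AE denominator is the Safety Set of Section 7.2.2: "all patients having received at least one dose of a study drug and at least one post-baseline safety evaluation". On duration, the Study Outline says: "Study treatment will last for a minimum of 90 consecutive days and as long as PN is indicated, up to 365 consecutive days". It also says: "The study ends after the Final Study Visit, latest on Day 366". Section 6.1 places the Final Study Visit on the day after the last dose, and Section 12.3.6 closes the observation period with that visit, apart from following unresolved events.

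Treatment can end before Day 91 (Section 7.3) or later. Section 10.3.4 sets stops for triglycerides, direct bilirubin, severe or clinical essential fatty acid deficiency (EFAD) and inadequate growth; for severe EFAD, "the patient must be permanently taken off study medication immediately". Weaning to enteral or oral nutrition is a further exit. The only time-based safety variable is the first Study Day with direct bilirubin above 2 mg/dL.

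**The concern.** The percentage of patients with at least one AE depends both on how often events occur and on how long patients are watched. Here the second part varies widely and ends under rules tied to outcomes. Randomisation balances patients at entry; it does not balance stays that the assigned lipid may then shorten. The protocol itself gives reasons why the stopping criteria could behave differently by arm. Section 4.1 reports greater bilirubin decreases with Smoflipid in two earlier studies, and notes its lower content of linoleic acid, an essential fatty acid.

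The study has no primary endpoint and no tests (Sections 6.2 and 7.2.1), so the descriptive tables are the result. Section 6.2 says the safety data should help prescribers know which events to anticipate. A percentage with no time base does this poorly, and the error can go either way: a longer-staying arm may look worse at the same rate, or an arm stopped early may look no worse despite a higher rate.

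**Working it through.** **Inputs from the plan.** 3 age groups × 2 arms × 24 = 144 patients, and 3 × 24 = 72 per arm, which reproduces Section 7.2.1. Intended treatment is 90 to 365 days. No AE rate, expected stay, alpha or power is given.

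**Assumed inputs.** Rates of 0.1 to 2 first events per patient-year, the same in both arms and constant over time; stays as in the table.

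**Model 1, fixed stay of t days, rate r per year:** P(at least one AE) = 1 − exp(−r × t/365).

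- r = 1, 180 days: 1 − exp(−0.493) = 38.9%, about 28 of 72.
- r = 1, 270 days: 1 − exp(−0.740) = 52.3%, about 38 of 72.
- 0.10 per month, 4 vs 8 months: 1 − exp(−0.4) = 33.0% vs 1 − exp(−0.8) = 55.1%.

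**Model 2, everyone stays 90 days, then stops at constant daily hazard h until Day 365.** If a fraction k is still treated at Day 365, h = −ln(k)/275 and mean stay = 90 + (1 − k)/h. With r now per day,

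P = 1 − exp(−90r) × [ h/(h+r) × (1 − exp(−275(h+r))) + exp(−275(h+r)) ].

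Example at 1 event per patient-year (r = 1/365): k = 0.4 gives h = 0.00333, mean stay 270 days and P = 50.5%; k = 0.5 gives h = 0.00252, mean stay 288 days and P = 53.0%.

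| Stays compared | Rate | Patients with an AE | Gap (points) |
|---|---|---|---|
| 288 vs 288 d (model 2) | 0.1 to 2 per year | identical | 0 |
| 270 vs 288 d (model 2) | 0.1 per year | 7.1% vs 7.6% | 0.5 |
| 270 vs 288 d (model 2) | 2 per year | 73.5% vs 76.1% | 2.6 |
| 250 vs 305 d (model 2) | 1 per year | 47.7% vs 55.3% | 7.6 |
| 180 vs 270 d (model 1) | 1 per year | 38.9% vs 52.3% | 13.3 |
| 4 vs 8 months (model 1) | 0.10 per month | 33.0% vs 55.1% | 22.1 |

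Gaps are taken before rounding.

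**Masking.** With stays of 180 and 270 days, the percentages coincide when the short-stay rate is 270/180 = 1.5 times the long-stay rate. For example, 1.5 per year over 180 days and 1 per year over 270 days both give 52.3%.

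**With patient-time.** Under the same constant rate, first events divided by time at risk have an expected ratio of 1.00 between arms, whatever the stays.

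**A related inconsistency.** The pre-Day 91 stop for parenteral nutrition covering under 60% of energy requires at least one month in the Study Outline and Sections 6.1, 9.4 and 10.4.2, but at least one week in Sections 7.3 and 11.2.4. This affects length of observation, and the passages must be reconciled.

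**The case against.** The strongest reply is that Section 7.2.3 never names AEs. It gives a generic rule and defers detail to the SAP, which may add exposure-adjusted rates. That is fair, but AEs fall under the rule as a listed target variable, and neither the deferral nor the allowance for summaries by Study Day commits to anything on exposure.

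Second, a reader might infer that the longer-staying arm will look less safe. The documents do not support that as a prediction: allocation is 1:1, blinded and within age cohort, no expected stay is given, and weaning is not obviously lipid-dependent. A reader might also take some 14 to 22 points as the expected distortion. Gaps of that order need large imbalances: under model 2, means of 4 vs 8 months require roughly 0% vs 27% of patients still treated at Day 365. A gap of 2 or 3 points would be lost in sampling error; at 50% and 72 per arm the standard error of a difference is √(2 × 0.25/72) = 8.3 points.

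Third, stops for bilirubin, EFAD or growth are not themselves hidden. Bilirubin incidence and timing, EFAD grade and growth z-scores are reported separately, termination reasons are recorded, and clinically significant laboratory values count as AEs. This stands for those events, but not for other AEs that a shorter stay leaves no time to observe.

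Fourth, rates per patient-month are imperfect. If events cluster early they inflate the short-stay arm, and they do not cure informative stopping. This also stands, and shapes the remedy.

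**Conclusion.** The concern holds in conditional form. As written, the plan's only AE summary mixes event rate with length of stay. If mean stay differs by arm, it will produce a gap at equal rates or can hide a real one. The size rests on assumed constant rates and assumed stays: none with equal stays, under 3 points at 270 vs 288 days, about 13 at 180 vs 270 days with 1 event per patient-year, and about 22 at 4 vs 8 months with 0.10 per month. This is a worthwhile, cheap improvement, not a defect that invalidates the study.

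Three further readings go beyond the documents:

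- **That replaced patients bias the comparison.** Section 7.3 replaces only those stopped for non-safety reasons, so bilirubin and triglyceride stops are not replaced, and nothing indicates that replacement will differ by arm.
- **That percentages cannot be compared with the neonatal and infant study in Section 4.1.** The 28 days there are the minimum parenteral nutrition requirement and the bilirubin endpoint window. No AE window and no AE comparison between the studies is stated.
- **That rates should displace percentages.** Nothing here requires that; the two belong side by side.

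**What to change.** In Section 7.2.3 and the SAP, before unblinding, commit to reporting beside the crude AE percentages:

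1. Patient-time at risk by arm and age group.
2. For AEs, SAEs and related AEs, patients with a first event per 100 patient-months at risk, with 95% confidence intervals, by arm and age group.
3. Cumulative incidence of first event over the common window Day 1 to Day 90, with treatment stopping handled as a competing event.

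Use total-event rates only if repeated episodes are individually dated, because Section 12.3 records like episodes as one AE.

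The cost is SAP wording, programming and extra tables. AEs and study drug administration are already recorded by study day (Sections 1, 10.3.4 and 11.2.3), so no new data are needed. The limit is that item 2 assumes a roughly constant hazard and does not fully remove informative stopping. Item 3 does not need a constant hazard and removes unequal follow-up after Day 90, which is why it belongs beside item 2. Stopping before Day 90 still lowers it, so the cumulative incidence of stopping should be shown with it.

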As Smoflipid and its components have been used widely and given world-wide with a very rare incidence of adverse drug reactions (ADRs)/serious adverse events (SAEs), no confirmatory hypotheses will be tested. All target variables will be analyzed in an exploratory manner presenting descriptive statistics. The trial will not be powered. To power this trial, selection of one single parameter would be required as a primary safety endpoint to show a clinically meaningful difference between the treatment groups (the treatment effect) in a reasonable sample size and trial duration. As mentioned above, both Smoflipid and Intralipid 20% provide parenteral lipids. Selecting a single parameter to power the study as a superiority study or as a non-inferiority study with a reasonable non-inferiority margin would be difficult because the similar treatment concept would require more patients than could be obtained under any reasonable circumstances due to very low incidence of adverse drug reactions.

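### Percentages that include a missing category fall as patients leave; use an evaluable base at each visit and cumulative incidence for PNALD/PNAC and EFAD

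*Combined protocol and SAP*

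**What the plan says.** Section 7.2.3 summarises categorical variables (binary and ordinal ones included) as counts and percentages, "including 'missing data' as valid category". In the same paragraph, numerical variables are summarised on the data available. The section adds: "Wherever useful, the summary statistics will be presented by Study Day". Confidence intervals are foreseen only where a mean and standard deviation are calculated, so a binary percentage is printed without one. Of the separate SAP it says: "It will also include information on the handling of missing values". No such SAP text is in the document reviewed.

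Section 5.2 defines PNALD/PNAC incidence as a count: "Number of patients in each treatment group with direct bilirubin levels > 2 mg/dL", confirmed by a second sample 7 days later. The companion time variable is the Study Day of the first raised value. EFAD is graded from the triene/tetraene ratio at 0.05, 0.20 and 0.40.

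Nothing confirmatory rests on these summaries. Section 7.2.1 states: "There is no primary outcome parameter and the study is not powered". Section 6.2 states: "no confirmatory hypotheses will be tested".

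**The concern.** Once missing is a category of its own, the category percentages add to 100% only if patients without a value are in the base. The printed event percentage then mixes two things: how often the event is seen among patients measured, and how many were measured.

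In this trial the second part changes by design. Treatment ends when PN or lipid is no longer needed (Sections 6.1 and 7.3). It also ends on the triglyceride, bilirubin, EFAD and growth rules of Section 10.3.4. The Final Study Visit follows the next day (Section 6.1), re-treatment after PN has ceased is not allowed (Section 11.2.4), and nobody is replaced after Day 90 (Section 7.3). The missing share in a by-Study-Day table can therefore only grow as patients leave. A child taken off for severe EFAD would be missing at every later visit, so the severe-EFAD percentage can fall because the case was removed.

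With no model, test or interval behind them, these percentages are what readers will compare between arms.

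**Working it through.** **Inputs.** Section 7.2.1 plans 24 patients per arm in each of three age groups: 24 × 2 × 3 = 144 in total, as stated, and 24 × 3 = 72 per arm. The documents give no event rate and no drop-out rate. All such rates below are assumptions.

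**Formula.** Let N be the patients in an arm, M those missing, O = N − M those observed, and E the events. With p = E/O and m = M/N:
- base including missing: E/N = p(1 − m)
- evaluable base: E/O = p

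**Illustration, 72 per arm.**

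| | Arm A | Arm B |
|---|---|---|
| Missing | 7 | 22 |
| Observed | 65 | 50 |
| Events | 13 | 10 |
| Base including missing | 13/72 = 18.1% | 10/72 = 13.9% |
| Evaluable base | 13/65 = 20.0% | 10/50 = 20.0% |

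**Range.** For equal p in both arms, the printed gap is p(m₂ − m₁). With 10% and 30% missing it is 0.20p:
- p = 5%: 1.0 point
- p = 10%: 2.0 points
- p = 20%: 4.0 points
- p = 30%: 6.0 points

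The ratio is 0.9/0.7 = 1.29 throughout. With equal missingness there is no gap: 12 missing in each arm and p = 20% gives 12/72 = 16.7% in both.

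**Within one age group.** With 24 per arm, 4 of 20 and 3 of 15 observed (20.0% in both) print as 4/24 = 16.7% and 3/24 = 12.5%. That gap of 4.2 points equals one patient (1/24 = 4.2%).

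**The opposite case.** Suppose the true rate over the study is 20% in both arms and every leaver is truly event-free, with 10% leaving one arm and 30% the other. The full base gives 20.0% in both. The observed-only base gives 0.20/0.9 = 22.2% and 0.20/0.7 = 28.6%. For an over-study incidence, the observed-only base can therefore create a difference of its own.

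**Side by side.** At one Study Day, mean direct bilirubin would use patients with a value, while the share above 2 mg/dL would use patients with and without one. The triene/tetraene ratio and its EFAD grade are split in the same way. No reason is given.

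**The case against.** Three stronger readings are tempting, and the documents support none of them.

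- A reader might infer that a patient without a value is counted as having no event. The text makes missing its own category, so a table would show yes, no and missing. Counts are required too, so the observed-only percentage can be recomputed and unequal missingness seen.
- A reader might infer that safety percentages are biased downward throughout. That needs leavers to carry the same risk as those who stay. Some leave because the gut has recovered (Section 9.4), and the opposite case above shows that the full base can then be the right one.
- A reader might infer a false difference between arms. That needs unequal missingness, and no drop-out figure is given, by arm or overall.

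Three further points also stand. Section 7.2.3 does not state the denominator in words, nor whether a patient who has left stays in later tables, and it leaves missing values to the SAP. PNALD/PNAC incidence is a count over the study, and nothing says that an event-free leaver is missing for it. The safety set requires a post-baseline safety evaluation, and the Final Study Visit repeats the monthly procedures apart from a limited blood-sampling exception. Few treated patients need be wholly without data.

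This limits the point without removing it. A SAP that follows Section 7.2.3 inherits the mixed base, and the printed percentage remains the one that depends on retention.

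**Conclusion.** A worthwhile and cheap improvement. Read naturally, Section 7.2.3 makes by-Study-Day percentages equal to p(1 − m), so they fall with departures and are comparable between arms only if retention is similar. Under the assumed rates (p from 5% to 30%, missing 10% against 30%), equal observed rates would print 1.0 to 6.0 points apart; with equal missingness the gap is zero. The actual size and direction are unknown.

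The visit tables and the over-study incidences need different remedies. At a visit, an evaluable base describes the patients measured that day, matches the treatment of numerical data, and loses nothing if the number missing is kept. Over the study, neither simple base is safe: follow-up varies up to 365 days and leaving can be linked to outcome. Section 5.2 offers only a patient count and the Study Day of first elevation, with no method for unequal follow-up.

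**What to change.** In Section 7.2.3, the SAP and the table shells:

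1. Base each visit-level percentage on patients with an evaluable value, print that denominator, and show the number missing by arm and Study Day as a separate count outside it. State that patients who have left are included in that count.
2. For PNALD/PNAC and for EFAD over the study, report cumulative incidence by arm with numbers at risk, beside the crude number of patients with the event. Do not use an observed-only denominator for these.
3. Prespecify how the end of study treatment for recovery (PN or lipid no longer indicated) is handled. As a competing event, the result is the share who develop the condition on study treatment. As censoring, it is the risk had treatment continued, and it assumes that leavers would have had the same later risk. If all leavers in the opposite case leave through recovery and nobody is censored, the competing-event version returns 20.0% in both arms.

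The cost is a few sentences, revised shells and modest extra programming before SAP sign-off. No new data are needed. The downside is sparse denominators at late visits, which must be shown.
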